### 3.2 Exclusion Criteria

1. Myocardial infarction within the past 12 months, or stable or unstable angina.
2. Systolic heart failure defined as left ventricular ejection fraction  $\leq 45\%$ .
3. Symptomatic valvular heart disease.
4. Prior chemotherapy for advanced or metastatic disease.
5. Known brain metastases.
6. Prior or second primary malignancies within the last two years (except carcinoma in situ of the cervix, non-metastatic prostate cancer, or basal cell or squamous cell carcinoma of the skin which were treated with local resection only; prior adjuvant androgen deprivation therapy in the case of prostate cancer is permitted, but current adjuvant androgen deprivation therapy is not).
7. Currently receiving any investigational agents.
8. A history of allergic reactions attributed to compounds of similar chemical or biologic composition to dextrazoxane or other agents used in the study.
9. Uncontrolled intercurrent illness including, but not limited to, ongoing or active infection, symptomatic congestive heart failure, or psychiatric illness/social situations that would limit compliance with study requirements.
10. Pregnant and/or breastfeeding. Patient must have a negative pregnancy test within 14 days of study entry.
11. Known HIV-positivity on combination antiretroviral therapy because of the potential for pharmacokinetic interactions with dextrazoxane. In addition, these patients are at

increased risk of lethal infections when treated with marrow-suppressive therapy. Appropriate studies will be undertaken in patients receiving combination antiretroviral therapy when indicated.

12. Prior treatment with anthracyclines.

### **3.3 Inclusion of Women and Minorities**

Both men and women and members of all races and ethnic groups are eligible for this trial.

## **4.0 REGISTRATION PROCEDURES**

**Patients must not start any protocol intervention prior to registration through the Siteman Cancer Center.**

The following steps must be taken before registering patients to this study:

1. Confirmation of patient eligibility
2. Registration of patient in the Siteman Cancer Center OnCore database
3. Assignment of unique patient number (UPN)

### **4.1 Confirmation of Patient Eligibility**

Confirm patient eligibility by collecting the information listed below:

1. Registering MD's name
2. Patient's race, sex, and DOB
3. Three letters (or two letters and a dash) for the patient's initials
4. Copy of signed consent form
5. Completed eligibility checklist, signed and dated by a member of the study team
6. Copy of appropriate source documentation confirming patient eligibility

### **4.2 Patient Registration in the Siteman Cancer Center OnCore Database**

All patients must be registered through the Siteman Cancer Center OnCore database.

### **4.3 Assignment of UPN**

Each patient will be identified with a unique patient number (UPN) for this study. All data will be recorded with this identification number on the appropriate CRFs.

## **5.0 TREATMENT PLAN**

### **5.1 Agent Administration**

Dexrazoxane will be given intravenously on an outpatient basis over 15 minutes on each day that doxorubicin is given. Dexrazoxane should be given no more than 30 minutes prior to administration of doxorubicin, which is typically given on Day 1 of a 21-day cycle. Dosing is a 10:1 ratio of dexrazoxane to doxorubicin; doxorubicin will be started at 75 mg/m^2, so dexrazoxane dosing would be 750 mg/m^2. Doxorubicin is being given as routine care; the administration is not dictated per protocol. Patients who are enrolled in the control group will receive institutional standard of care therapy.

In the event of a national shortage of dexrazoxane, 72-hour infusional doxorubicin can be used instead of dexrazoxane and bolus doxorubicin.

## **5.2 General Concomitant Medication and Supportive Care Guidelines**

Premedications and supportive care may be given routinely as needed to prevent or treat doxorubicin-related toxicities or adverse reactions.

## **5.3 Women of Childbearing Potential**

Women of childbearing potential (defined as women with regular menses, women with amenorrhea, women with irregular cycles, women using a contraceptive method that precludes withdrawal bleeding, and women who have had a tubal ligation) are required to have a negative pregnancy test within 14 days prior to the first dose of study treatment.

Female and male patients (along with their female partners) are required to use two forms of acceptable contraception, including one barrier method, during participation in the study and for one month following the last dose of study treatment.

If a patient is suspected to be pregnant, study treatment should be immediately discontinued. In addition a positive urine test must be confirmed by a serum pregnancy test. If it is confirmed that the patient is not pregnant, the patient may resume dosing.

If a female patient or female partner of a male patient becomes pregnant during therapy or within one month after the last dose of study treatment, the investigator must be notified in order to facilitate outcome follow-up.

## **5.4 Duration of Therapy**

If at any time the constraints of this protocol are considered to be detrimental to the patient's health and/or the patient no longer wishes to continue protocol therapy, the protocol therapy should be discontinued and the reason(s) for discontinuation documented in the case report forms.

In the absence of treatment delays due to adverse events, treatment with dexrazoxane may continue as long as treatment with doxorubicin continues or until one of the following criteria applies:

- Documented and confirmed disease progression
- Death
- Adverse event(s) that, in the judgment of the investigator, may cause severe or permanent harm or which rule out continuation of study drug
- General or specific changes in the patient's condition render the patient unacceptable for further treatment in the judgment of the investigator
- Suspected pregnancy
- Serious non-compliance with the study protocol
- Lost to follow-up
- Patient withdraws consent
- Investigator removes the patient from study
- The Siteman Cancer Center decides to close the study

Patients who prematurely discontinue treatment for any reason will be followed as indicated in the study calendar.

### **5.5 Duration of Follow-up**

Patients will be followed every 3 months for up to five years or until death, whichever occurs first. Patients removed from study for unacceptable adverse events will be followed until resolution or stabilization of the adverse event. Patients who go off study due to toxicities will be followed until progression of their disease.

## **6.0 DOSE DELAYS/DOSE MODIFICATIONS**

Dosing of dexrazoxane should be consistent with dosing of doxorubicin to maintain the 10:1 ratio; if dosing of doxorubicin is reduced as part of the patient's routine care, dosing of dexrazoxane should be reduced proportionally.

Dosing of dexrazoxane should be reduced in patients with moderate to severe renal impairment (creatinine clearance levels < 40 mL/min) by 50%, i.e., reducing the dexrazoxane to doxorubicin ratio from 10:1 to 5:1.

In the event of a national shortage of dexrazoxane, 72-hour infusional doxorubicin can be used in place of dexrazoxane and bolus doxorubicin.

All dose reductions should be discussed with the Principal Investigator.

## **7.0 REGULATORY AND REPORTING REQUIREMENTS**

The entities providing oversight of safety and compliance with the protocol require reporting as outlined below.

The Washington University Human Research Protection Office (HRPO) requires that all events meeting the definition of unanticipated problem or serious noncompliance be reported as outlined in Section 7.2.

## 7.1 Definitions

### 7.1.1 Adverse Events (AEs)

**Definition:** any unfavorable medical occurrence in a human subject including any abnormal sign, symptom, or disease. For the purposes of this study, adverse events related to doxorubicin are not considered reportable. However, all AEs will be tracked in OnCore. For purposes of data collection, the study drug is dexrazoxane.

**Grading:** the descriptions and grading scales found in the revised NCI Common Terminology Criteria for Adverse Events (CTCAE) version 4.0 will be utilized for all toxicity reporting. A copy of the CTCAE version 4.0 can be downloaded from the CTEP website.

**Attribution (relatedness), Expectedness, and Seriousness:** the definitions for the terms listed that should be used are those provided by the Department of Health and Human Services' Office for Human Research Protections (OHRP). A copy of this guidance can be found on OHRP's website:

<http://www.hhs.gov/ohrp/policy/advevntguid.html>

### 7.1.2 Serious Adverse Event (SAE)

**Definition:** any adverse drug experience occurring at any dose that results in any of the following outcomes:

- Death
- A life-threatening adverse drug experience
- Inpatient hospitalization or prolongation of existing hospitalization
- A persistent or significant disability/incapacity (i.e., a substantial disruption of a person's ability to conduct normal life functions)
- A congenital anomaly/birth defect
- Any other experience which, based upon appropriate medical judgment, may jeopardize the subject and may require medical or surgical intervention to prevent one of the outcomes listed above

### 7.1.3 Unexpected Adverse Experience

**Definition:** any adverse drug experience, the specificity or severity of which is not consistent with the current investigator brochure (or risk information, if an IB is not required or available).

### 7.1.4 Life-Threatening Adverse Experience

**Definition:** any adverse drug experience that places the subject (in the view of the investigator) at immediate risk of death from the reaction as it occurred, i.e., it does not include a reaction that, had it occurred in a more severe form, might have caused death.

### 7.1.5 Unanticipated Problems

**Definition:**

- unexpected (in terms of nature, severity, or frequency) given (a) the research procedures that are described in the protocol-related documents, such as the IRB-approved research protocol and informed consent document; and (b) the characteristics of the subject population being studied;
- related or possibly related to participation in the research (“possibly related” means there is a reasonable possibility that the incident, experience, or outcome may have been caused by the procedures involved in the research); and
- suggests that the research places subjects or others at a greater risk of harm (including physical, psychological, economic, or social harm) than was previously known or recognized.

### 7.1.6 Noncompliance

**Definition:** failure to follow any applicable regulation or institutional policies that govern human subjects research or failure to follow the determinations of the IRB. Noncompliance may occur due to lack of knowledge or due to deliberate choice to ignore regulations, institutional policies, or determinations of the IRB.

### 7.1.7 Serious Noncompliance

**Definition:** noncompliance that materially increases risks, that results in substantial harm to subjects or others, or that materially compromises the rights or welfare of participants.

### 7.1.8 Protocol Exceptions

**Definition:** A planned deviation from the approved protocol that are under the research team’s control. Exceptions apply only to a single participant or a singular situation.

Pre-approval of all protocol exceptions must be obtained prior to the event.

## 7.2 Reporting to the Human Research Protection Office (HRPO) at Washington University

The PI is required to promptly notify the IRB of the following events:

- Any unanticipated problems involving risks to participants or others which occur at WU, any BJH or SLCH institution, or that impacts participants or the conduct of the study.
- Noncompliance with federal regulations or the requirements or determinations of the IRB.
- Receipt of new information that may impact the willingness of participants to participate or continue participation in the research study.

These events must be reported to the IRB within **10 working days** of the occurrence of the event or notification to the PI of the event. The death of a research participant that qualifies as a reportable event should be reported within **1 working day** of the occurrence of the event or notification to the PI of the event.

### **7.3 Reporting to the Quality Assurance and Safety Monitoring Committee (QASMC) at Washington University**

The PI is required to notify the QASMC of any unanticipated problem occurring at WU or any BJH or SLCH institution that has been reported to and acknowledged by HRPO as reportable. (Unanticipated problems reported to HRPO and withdrawn during the review process need not be reported to QASMC).

QASMC must be notified within 10 days of receipt of IRB acknowledgment via email to a QASMC auditor.

### **7.4 Timeframe for Reporting Required Events**

Adverse events will be tracked for 30 days following the last day of study treatment. For the purposes of this protocol, adverse events considered possibly, probably, or definitely related to doxorubicin are not reportable.

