### **1.3.1 Cardiotoxicity and Anthracyclines**

The most concerning toxicity of anthracyclines is cardiotoxicity. Anthracycline-induced cardiotoxicity ranges from subclinical left ventricular dysfunction to severe cardiomyopathy with heart failure. Cardiotoxicity may occur acutely within the first week of treatment, early within one year of completing therapy, or late after one year of completing anthracycline treatment.

The cardiotoxic effects of doxorubicin have been well established in studies dating back decades . The estimated incidence of heart failure for patients on doxorubicin receiving a cumulative dose of 400-550 mg/m^2 range widely from a relatively low 3-7% by Von Hoff et al 1979 to a significantly higher 27% by Speyer et al 1992. At higher doses around 1000 mg/m^2 as many as half of patients may experience the cardiotoxic effects .

The exact mechanism of anthracycline-induced cardiotoxicity is not entirely known. It has traditionally been believed that the cardiotoxic effects of have been mediated by redox cycling and the generation of reactive oxygen species; newer evidence suggests that it may be specifically mediated by topoisomerase-IIβ in cardiac myocytes . An additional mechanism may include accumulation of mitochondrial iron leading to increased reactive oxygen species inside the cardiac myocyte .

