## **2.2 Secondary Objectives**

1. To determine cardiac-related mortality in patients with metastatic soft tissue sarcoma who are treated with doxorubicin in combination with dextrazoxane.
2. To determine incidence of heart failure or cardiomyopathy in patients with metastatic soft tissue sarcoma who are treated with doxorubicin in combination with dextrazoxane.
3. To evaluate additional echocardiogram parameters of left ventricular ejection fraction to determine if either 3D echocardiogram or ventricular strain is able to serve as an early marker of cardiac dysfunction compared to 2d echocardiogram modified Simpson's biplane method of LVEF.

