## **9.3 Measurement of Brain-type Natriuretic Peptide (BNP)**

Patients receiving dexrazoxane will have blood drawn to measure BNP. Blood will be drawn in an EDTA (lavender top) tube as a baseline measurement before Cycle 1 and then after a cumulative dose of 300mg/m^2 of doxorubicin. In patients continuing to receive doxorubicin after a cumulative dose of 300mg/m^2, a BNP will be measured every 6 weeks. A total of 2mL of blood needs to be collected in each EDTA tube or the lab may be added onto a basic metabolic panel or complete metabolic panel if done prior to chemotherapy. BNPs will be performed as a clinical test to evaluate early appearance of cardiac toxicity and clinically relevant LV systolic deterioration. An increase of BNP above normal or baseline will trigger additional evaluation of cardiac function (another echocardiogram) and possibly evaluation by cardiology per treating oncologist's discretion.

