## 11.0 DATA SUBMISSION SCHEDULE

Case report forms with appropriate source documentation will be completed according to the schedule listed in this section.

Case Report Form	Submission Schedule
Original Consent Form	Prior to registration
On-Study Form	Prior to starting treatment
Treatment Form	Every cycle
Toxicity Form	Continuous
Treatment Summary Form	Completion of treatment
Follow Up Form	Every 3 months for up to 5 years
Tumor Measurement Form	Baseline, end of every even numbered cycles, EOT, and for all standard of care disease assessments done during follow up until documented progression.
Echocardiogram & Holter Monitor Form	Baseline, and Day 1 of every odd-numbered cycle starting with Cycle 3
hscTNI & Galectin-3 Form	Day 1 of every cycle
BNP Form	Baseline and Day 1 of every odd-numbered cycle starting with Cycle 5

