## **14.3 Secondary Endpoints**

Cardiac-specific mortality will be analyzed using Kaplan-Meier models to estimate median times to these events, as well as the proportion experiencing an event at 3, 6, 9 and 12 months.

Agreement between 3D and 2d echocardiogram biomarkers will be described using Bland-Altman plots, which plot the mean of two measurements on the same individual against the difference of those measurements. If the values are reasonably Gaussian, the standard  $\pm 2$  standard deviations will be used as the limits of agreement. If the values are non-Gaussian, bootstrap estimates will be used to define the limits of agreement.

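### The heart-failure objective has no collection rule beyond 30 days after the last dose, no cardiac test scheduled in follow-up and no planned analysis, so later events are likely to be missed

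*Combined protocol and SAP*

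**What the plan says.** Section 2.2 sets the objective: "To determine incidence of heart failure or cardiomyopathy in patients with metastatic soft tissue sarcoma" treated with the combination. It gives neither a time horizon nor an event definition.

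Section 1.3.1 describes three periods of anthracycline cardiotoxicity. One is acute, in the first week. The other two are "early within one year of completing therapy, or late after one year of completing anthracycline treatment".

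Section 7.4 sets the collection window: "Adverse events will be tracked for 30 days following the last day of study treatment". No exception is made for cardiac events.

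Follow-up itself runs much longer. Section 5.5 says "Patients will be followed every 3 months for up to five years or until death, whichever occurs first", and section 11.0 schedules a Follow Up Form "Every 3 months for up to 5 years". The fields of that form are not described.

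Cardiac testing follows the treatment cycles. Section 11.0 schedules the echocardiogram and Holter form at "Baseline, and Day 1 of every odd-numbered cycle starting with Cycle 3". Under section 9.3, once 300 mg/m² of doxorubicin has been given, "a BNP will be measured every 6 weeks", but only in patients who continue doxorubicin.

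On analysis, section 14.3 says "Cardiac-specific mortality will be analyzed using Kaplan-Meier models to estimate median times to these events", with proportions at 3, 6, 9 and 12 months. It does not mention heart-failure incidence.

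**The concern.** Two of the protocol's own three periods of cardiotoxicity lie almost wholly after the one stated collection window closes. A site could follow section 7.4 exactly and have no instruction to record heart failure that first appears 3 or 9 months after the last dose. The trial might then report a short-window figure as the answer to an objective that has no time limit.

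Comparability is also at stake. Section 9.1 adds banking-study controls whose charts are reviewed for cardiac function and symptomatic heart failure. No window is stated for that review, so events may be ascertained over different periods in the two groups.

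**Working it through.** The plan states no expected rate, sample size or precision for heart-failure incidence, so there is no figure to reproduce. The check has two parts.

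**1. Routes by which a new cardiac event after treatment could be recorded**

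- Adverse-event tracking (7.4): closes 30 days after the last study treatment. Section 7.1.1 says all adverse events are entered in OnCore but sets no longer window.
- Follow-up of adverse events (5.5): covers events that led to removal, until they resolve or stabilize. New events are not mentioned.
- Echocardiogram (9.1, 10.1, 11.0): section 9.1 says every six weeks without an end point. The calendar and form schedule place it on Day 1 of odd-numbered cycles from Cycle 3, with none at end of treatment or in follow-up. A patient who stops after six cycles has the last calendar echocardiogram before dose 5.
- BNP (9.3): continues only while doxorubicin continues.
- Follow-up visits (5.5, 10.1, 11.0): history and physical with performance status, plus the Follow Up Form. No text says that new heart failure is recorded there.
- Analysis (14.3): cardiac death only.

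No route both extends past 30 days and states that a new non-fatal cardiac event is recorded.

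**2. Illustration of the time left uncovered**

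Inputs from the documents: doxorubicin is typically given on Day 1 of a 21-day cycle (5.1); median survival is 11 to 15 months (1.2); the window is 30 days (7.4). Assumptions: six doses, and exponential survival S(t) = exp(−ln 2 × t / median). At-risk time is approximated by time alive.

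- Last dose: 5 × 21 = 105 days (week 15).
- Window closes: 105 + 30 = 135 days; 135 / 30.44 = 4.43 months.
- Share of at-risk time in months 0 to 12 outside the window: [S(4.43) − S(12)] / [1 − S(12)].

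| Median survival | S(4.43) | S(12) | Share outside window |
|---|---|---|---|
| 11 months | 0.756 | 0.469 | 0.287 / 0.531 = 54% |
| 15 months | 0.815 | 0.574 | 0.240 / 0.426 = 56% |

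Sensitivity to treatment length: with the last dose at 2.8 months the share outside is 60% to 62%; at 6.0 months it is 33% to 35%.

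Section 1.3.1 counts from completion of therapy. On that clock, the share of first-year time alive that falls inside the 30-day (0.986-month) window is [1 − S(0.986)] / [1 − S(12)], which under exponential survival does not depend on treatment length. It is 0.060 / 0.531 = 11% at a median of 11 months, and 0.045 / 0.426 = 10% at 15 months.

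These are shares of time, not of events. Converting them to missed events needs the hazard of heart failure after treatment, which the documents do not give.

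**The case against.** The strongest reply is that section 7.4 belongs to the regulatory reporting section and does not claim to govern endpoint ascertainment. Patients are examined every 3 months for up to five years, a form is completed each time, and a history and physical can reveal symptomatic heart failure. The plan to report cardiac death at 3 to 12 months shows that some cardiac outcome collection beyond 30 days is intended. The objective is also descriptive and unpowered, and the primary PFS analysis is untouched.

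Much of this stands. A reader might infer that late heart failure will certainly go unrecorded. The documents do not support that, because the Follow Up Form's fields are not shown. A reader might also infer that the result is biased in favour of dexrazoxane. Objective 2 names no comparator, the ten enrolled controls have closely similar calendars, and the chart review has no stated window, so a difference in ascertainment is possible but not shown. Nor can a corrected incidence be given: section 1.3.1 cites heart-failure rates from 3-7% to 27% for doxorubicin at 400-550 mg/m², and any late share applied to them would be invented.

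What the reply does not supply is a definition, a source, a window or an estimator for objective 2. It also offers no planned means of finding cardiomyopathy without symptoms after treatment.

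**Conclusion.** The concern holds as a gap between the objective and its data collection. As written, the likely result is an on-treatment plus 30-day incidence that misses later events; under-counting is likely, not established. Under the six-dose and exponential-survival assumptions, about 54% to 56% of at-risk time in the first 12 months from treatment start falls outside the window. The size of that share depends on those assumptions; the gap in the rules does not. This should be fixed, but as a low-cost improvement to a descriptive secondary objective: it does not threaten the primary endpoint.

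**What to change.** - **Section 2.2:** define heart failure or cardiomyopathy and state the time horizon. If only on-treatment plus 30-day incidence is intended, say so here; the collection changes below are then not needed, but section 14.3 still needs an analysis for that window.
- **Section 7.4:** exempt new heart failure or cardiomyopathy from the 30-day limit.
- **Follow Up Form (11.0):** add an item for date, type (symptomatic or LVEF-based) and source. Complete it from the history and physical and any clinically obtained echocardiogram, for at least 12 months after the last doxorubicin dose and through planned follow-up.
- **Section 14.3:** report cumulative incidence at 3, 6, 9 and 12 months from a named time origin, with death without heart failure as a competing event. The competing event matters because median survival is only 11 to 15 months. Show the on-treatment plus 30-day figure separately.
- **Section 9.1:** apply the same definition and window to the chart-review controls.

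The cost is one form item and a few sentences, with no new visit or scan. The reported incidence may be higher. Late cardiomyopathy without symptoms would still be missed without scheduled imaging, and the report should state that as a limitation.
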